Research program

Vacuum-formed retainer versus bonded cuspid-to-cuspid retainer to prevent relapse after orthodontic treatment– A randomized controlled trial about stability and patients' perceptions

NCT03070444

PhD student [name], Senior consultant, Department of orthodontics, Gävle

Supervisor: [name], Associate professor, PhD, Department of oral and maxillofacial surgery, Umeå University

Assistant supervisor: [name], Senior consultant, Department of orthodontics, Gävle

Assistant supervisor: [name], Associate professor, Department of oral and maxillofacial surgery, Umeå University

Aim

The overall objective of this randomized trial is to evaluate and compare stability after orthodontic treatment with an Essix retainer and a bonded cuspid-to-cuspid retainer (CTC) respectively in the mandibular arch and longitudinally follow these patients over time up to 5 years. The patients' perceptions of the two methods are also evaluated with questionnaires during the follow-up period.

A further aim of this study is to analyze the relationship between diagnosis, treatment outcome, treatment time, age at start of treatment and stability with an Essix-retainer in the maxilla.

Introduction

For successful orthodontic treatment the teeth need to be maintained in their corrected position after removal of orthodontic appliances. According to Proffit (2012) orthodontic treatment results are potentially unstable and therefore retention is necessary for three major reasons: the gingival and periodontal tissues require time for reorganization, growth changes can cause relapse and pressure from soft tissues i.e tongue, lips and cheeks can cause the teeth to move or rotate in an unwanted direction.

To prevent relapse patients are provided with fixed or removable retainers. The advantage of fixed retainers is that they are bonded to the palatal or lingual surfaces and do not depend on the patient's compliance. On the other hand these retainers demand good oral hygiene procedures to avoid plaque and calculus accumulation and the bonding procedure is time consuming and technique sensitive (Dahl and Zachrisson, 1991).

Hawley retainers are the most commonly used removable appliance since it was introduced in 1919, almost a century ago (Atack et al, 2007). However, patients have difficulties with speech, are embarrassed over the esthetics and cooperate less the first six months in retention (the critical phase) with the Hawley retainer (Hichens et al, 2007) (Bennett and Tulloch, 1999).

In the early 1990s thermoplastic vacuum-formed retainers were introduced and became very popular (Sheridan et al, 1993). Essix retainers are aesthetically well accepted, comfortable and less expensive than bonded retainers or Hawley retainers. Lindauer and Shoff (1998) and Rowland et al (2007) showed that vacuum-formed retainers are more effective than Hawley devices to maintain teeth in their new position after 6 months of retention.

In the literature the wear regimen of Essix retainers is not standardized. Lindauer and Shoff recommended 3 months full time wear and thereafter at night while Rowland et al recommended only one week full time wear. Jäderberg et al (2012), however, found no significant difference between full time wear for 3 months and 1 week, respectively, followed by night time. Their conclusions agree with the finding of Thickett and Power (2010) that there is no difference in the full time vs. part time wear regimen.

Transection of fibrous tissue (supra-alveolar fibers) to prevent relapse has been described already in the 1960s. Reitan (1967) observed that orthodontically derotated teeth are more

unstable and due to supra-alveolar tissue contraction rotational relapse may occur even after a retention period of more than 230 days. A long-term prospective study by Edwards (1988) showed that circumferential supracrestal fiberotomy (CSF) could alleviate dental relapse, especially of rotated teeth. Side effects such as clinically significant increase of periodontal sulcus depth or decrease in the labially attached gingiva were not observed.

There are several studies published investigating the effectiveness of bonded retainers and removable appliances to maintain tooth position after orthodontic treatment. Nevertheless, a systematic review by Littlewood et al (2006) stated that there is no evidence concerning the most appropriate retention strategy. They concluded that further research with well-designed randomized controlled trials to compare the effectiveness of different retention appliances is needed.

Only a few studies have analyzed patients' perception of orthodontic treatment (Bennett et al 1999, Hichens 2007, Feldmann et al 2012). Very few studies have analyzed patients' perception of retention appliances. Kumar and Bansal (2011) compared in a prospective study the effectiveness and acceptability of Essix and Begg retainers. They found that both appliances allowed some relapse but the differences were small and not clinically significant. The patients liked the comfort and appearance of the Essix retainer and preferred the Begg retainer for chewing and biting.

Although retention is a decisive factor for successful orthodontic treatment there are no evidence-based recommendations in the literature for retention appliances considering diagnoses before treatment such as vertical and skeletal deviations, the type of orthodontic movement (e.g. expansion or extraction cases) or for patients treated with fixed appliances and orthognathic surgery. Especially for patients with orthognathic surgery the choice of retention method and prevention of relapse are crucial since both skeletal and dental changes occur during treatment.

Materials and methods

The study is conducted at the Orthodontic Clinic, Gävle, Sweden and consists of 104 patients. All patients are treated with fixed appliances in the upper and lower jaw (standard .022 straight wire), both with and without extractions.

Patients treated with Rapid Maxillary Expansion (RME), orthognathic surgery, segmented appliance and patients with syndromes or agenesis of a mandibular incisor were excluded from the trial.

All patients who meet the inclusion criteria are invited to enter the trial. One experienced orthodontist (AK) provides the patients and parents with both oral and written information about the study protocol. After written consent is obtained from both the patient and parent the patients are randomized in blocks and stratified by gender into two groups. The allocation sequence is computer generated by a statistician at Gävleborg Count Hospital and concealed in opaque envelopes until randomization.

The patients are randomized into two groups with 52 patients in each group. All patients have Essix retainers in the maxilla covering all erupted teeth. The extension of the Essix retainers in the mandible covers only the dentition from first premolar to first premolar. The CTC-retainer is bonded to lingual surfaces of the mandibular canines.

Patients with rotated lower incisors (more than 30 degree) are treated with circumferential supracrestal fiberotomy 2 weeks prior to retention.

Group A: Retention with a CTC in the mandible and Essix retainer in the maxilla.

Two weeks before debonding an impression of the mandibular jaw is taken in order to manufacture the CTC retainer. The CTC-retainer is bonded to the canines directly after debonding. The Essix retainer is manufactured on dental casts after debonding and handed out to the patients the same day. The patients are instructed to wear the Essix retainer full-time the first week and thereafter night only.

Group B: Retention with Essix retainers in the maxilla and mandible.

The Essix retainers are manufactured on dental casts after debonding and handed out to the patients the same day. The patients are instructed to wear the Essix retainers full-time the first week and thereafter night only.

Dental cast are obtained at the debond appointment (T1) and at the follow-up controls after six months (T2), 18 months (T3) and 5 years (T4) for both groups. All measurements on casts are made with an electronic digital calliper to the nearest 0.25 mm. Comparisons within and between groups are performed.

Stability after retention is also analyzed depending on diagnoses before treatment and treatment outcome.

Outcome measures on the dental casts are as follow:

- Little's irregularity index
- Intercanine width
- Intermolar width
- Arch length
- Overjet
- Overbite

To assess measurement precision and reliability, 30 randomly selected dental casts are measured by the same examiner at a five weeks interval.

At the visit two weeks in retention and at the follow-up visits after 6, 18 and 60 months the patients assessed questionnaires in order to evaluate their experience of retention with an Essix retainer and a CTC respectively. The questionnaires include self-report questions from a previous study where reliability and face validity were found to be acceptable (Feldmann et al 2007). In addition, a few questions modified for this study are included. The fit of the retainers and the CTC are checked at each visit. All questionnaires are evaluated and compared between the two groups

Statistical analysis

Descriptive statistics are calculated for both groups (median, interquartile ranges, and test for normal distribution). The post-treatment changes are described by comparing measurements at debond (T1), after 6 months (T2), after 18 months (T3), and after 5 years (T4). Generalized estimating equations (GEE) are used to estimate the effect of the two treatment groups over time for the outcome variables. In the GEE analysis, all digital measurements, extraction therapy, sex, retention group, and time and the interaction of time with retention group are tested as explanatory variables (predictors). The GEE correlation structure is set to autoregressive, a convenient option for models with time-dependent observations.

Mann-Whitney U tests are used to analyse and compare the answers on questionnaires for the VFR/VFR and VFR/CTC group. Spearman's correlation coefficient is calculated to determine the relationship between patients' perceptions, self-reported VFR compliance, and LII. Demographic data are analysed with cross tabulations. P-values less than 0.05 are considered statistically significant.

Ethical considerations

All patients and parents are given oral and written information and sign a written consent before being included in the trial. The participation is voluntary and patients can leave the trial at any time without giving reasons.

Both of the tested retention-appliances are common and used frequently in orthodontic practices. The impressions at the follow-up visits are additional for this study.

The Ethics Committee of Uppsala (Regionala etikprövningsnämnden) approved the study protocol (diarienummer: 2009/177).

Research projects:

1. Effectiveness of Essix retainer versus bonded CTC in the mandibular arch after 6 and 18 months.

Aim: The aim of this project is to evaluate and compare stability in the mandibular arch 6 and 18 months after retention with an Essix retainer compared to retention with a bonded cuspid-to-cuspid retainer (CTC).

Material and methods: 104 patient are randomized into 2 groups; CTC (group A) and Essix retainer (group B). Little's Irregularity Index, intercanine width, intermolar width, arch length, overjet and overbite are measured on dental casts and analysed at the debond appointment, after 6 months and after 18 months.

The null hypothesis is that there is no difference in retention capacity between Essix retainer and cuspid-to-cuspid retainer.

The results from this study will be presented at the Swedish Dental Congress in 2018.

2. Evaluation of patients' perception of the retention appliances by questionnaires after 6 months and 18 months.

Aim: The aim of this project is to evaluate and compare patients' perception of their retention with an Essix retainer compared to retention with a bonded cuspid-to-cuspid retainer (CTC) 6 and 18 months after debonding.

Material and methods: 104 patients assessed a questionnaire after debonding and at the follow-up visit after six and 18 months to evaluate their experience of retention with an Essix retainer and a CTC respectively.

The null hypothesis is that there is no difference in patients' perception between Essix retainer and cuspid-to-cuspid retainer.

The results from this study will be presented at the Swedish Dental Congress in 2019.

3. Long-term stability in the mandibular arch after 5 years of retention.

Aim: The aim of this project is to evaluate and compare stability in the mandibular arch 5 years after retention with an Essix retainer compared to retention with a bonded cuspid-to-cuspid retainer (CTC).

Material and methods: 104 patients are randomized into 2 groups; CTC (group A) and Essix retainer (group B). Little's Irregularity Index, intercanine width, intermolar width, arch length, overjet and overbite are measured on dental casts and analysed after 5 years of retention.

The null hypothesis is that there is no difference in retention capacity between Essix retainer and cuspid-to-cuspid retainer.

The results from this study will be presented at the Swedish Dental Congress and the European Orthodontic Society Congress in 2021.

4. Retention stability in the maxilla depending on the diagnoses before treatment and on the treatment outcome after fixed orthodontic appliances.

Aim: The aim of this project is to evaluate and compare stability in the maxilla 6 months, 18 months and 5 years after retention with an Essix retainer.

Material and methods: Dental casts of 104 patients are measured and analyzed concerning overbite, overjet, intercanine width, intermolar width and arch length after 6 months, 18 months and 5 years of retention.

The null hypothesis is that there is no difference in retention capacity for Essix retainer in the maxilla concerning diagnosis before treatment, treatment outcomes, treatment time and age at start of treatment.

Relevance

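### Rounding every cast measurement to 0.25 mm adds a small, avoidable error to the change scores, larger for any outcome summed from several readings

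*Combined protocol and SAP*

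**What the plan says.** Materials and methods sets the recording rule: "All measurements on casts are made with an electronic digital calliper to the nearest 0.25 mm". It applies to all six outcomes listed there: "Little's irregularity index", intercanine width, intermolar width, arch length, overjet and overbite. The documents nowhere mention a finer unit, a reason for the step, the calliper's display resolution or the keeping of unrounded values. They also do not say how many readings make up LII or arch length.

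The same section plans a repeatability check: "To assess measurement precision and reliability, 30 randomly selected dental casts are measured by the same examiner at a five weeks interval". It also plans comparisons both within and between groups.

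Statistical analysis describes post-treatment change by comparing debond (T1) with 6 months (T2), 18 months (T3) and 5 years (T4), and adds: "Generalized estimating equations (GEE) are used to estimate the effect of the two treatment groups over time for the outcome variables". No SD, target difference or power is given.

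**The concern.** Each change compares two rounded readings, or two sums of rounded readings. Rounding discards information that an electronic calliper may already show, and the loss grows with the number of readings summed into an outcome. The comparison rests on a modest sample ("The patients are randomized into two groups with 52 patients in each group"), and with no SD in the documents a reader cannot tell whether a 0.25 mm step is fine enough for the changes expected. What is at stake is precision: slightly wider intervals and slightly lower power, mostly if the changes vary little between patients.

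**Working it through.** The plan has no sample-size calculation or error figure to reproduce.

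**Inputs from the documents.** Step w = 0.25 mm; 52 patients per arm, 104 in total; significance level 0.05 ("P-values less than 0.05 are considered statistically significant").

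**Assumed inputs.** Two-sided test; k readings per outcome, with k = 1 or 5 and k = 3 in between; SD of true change 0.5, 1.0 or 1.5 mm; examiner SD e = 0.10 to 0.20 mm per reading.

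**1. Rounding error.** Variance per reading v = w²/12 = 0.0625/12 = 0.00521 mm².
- One reading: SD √0.00521 = 0.072 mm, maximum 0.125 mm.
- Change, one reading per visit: √(2 × 0.00521) = 0.102 mm.
- Change, five readings per visit: √(10 × 0.00521) = 0.228 mm.

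**2. Equivalent patients lost.** Variance of a change without rounding: B = SD² + 2ke². Variance added by rounding: A = 2kv. Patients lost = 104 × A/(B + A).
- Example, k = 5, SD 0.5, e = 0.10: B = 0.25 + 0.10 = 0.35; A = 0.0521; 104 × 0.0521/0.4021 = 13.5.
- Example, k = 1, same SD and e: B = 0.25 + 0.02 = 0.27; A = 0.0104; 104 × 0.0104/0.2804 = 3.9.

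The range in each cell runs from e = 0.10 to e = 0.20.

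| Readings (k) | SD 0.5 mm | SD 1.0 mm | SD 1.5 mm |
|---|---|---|---|
| 5 | 13.5–7.7 | 4.7–3.7 | 2.3–2.0 |
| 3 | 9.5–6.2 | 3.0–2.6 | 1.4–1.3 |
| 1 | 3.9–3.2 | 1.05–0.99 | 0.48–0.46 |

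**3. Interval width and power.** The 95% interval widens by √(1 + A/B) − 1. For k = 5 this is 7.2%–3.9% at SD 0.5 and 2.3%–1.8% at SD 1.0. Power is for a two-sample t-test with 52 per arm and an effect set to give 0.80 without rounding.
- k = 5: power falls to 0.743–0.769 at SD 0.5 and 0.782–0.786 at SD 1.0.
- k = 1: power falls to 0.785–0.788 at SD 0.5 and 0.796 at SD 1.0.

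**4. Check against a GEE model.** In simulated complete data (60 trials per setting, four visits, autoregressive structure, time-by-group interaction, sex and extraction), the loss for k = 5 was 13.1 and 7.1 patients at SD 0.5 (e = 0.10 and 0.20), and 4.9 and 3.4 at SD 1.0. This agrees with the formula. The simulated model left out the cast measurements that the plan also lists as predictors, so it supports the formula but does not test the full planned model.

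**5. The 30-cast check.** For one distance measured twice under the 0.25 mm rule, reported method error against actual error of a recorded reading was:
- e = 0.10: 0.123 against 0.123 mm
- e = 0.20: 0.213 against 0.213 mm
- e = 0.05: 0.084 against 0.088 mm
- e = 0.02: 0.053 against 0.075 mm

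Over the examiner range used here, the check reports the right quantity.

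**6. What a finer step recovers.** For k = 5, SD 0.5 and e = 0.10, a 0.1 mm step leaves a loss of 2.4 patients and a 0.01 mm step 0.02. If T4 alone is read finely and T1 stays at 0.25 mm, the added variance for the T1–T4 change is 5v = 0.0260. At SD 0.5 the loss is then 104 × 0.0260/0.3760 = 7.2 (e = 0.10) or 104 × 0.0260/0.6760 = 4.0 (e = 0.20); at SD 1.0 it is 2.4–1.9. About half the loss remains.

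**The case against.** The strongest reply is that the plan contains no error: it states a recording step openly and applies it alike in both arms. Every SD behind the loss figures is assumed, and 13.5 patients is the worst corner of the grid. At an SD of change of 1.0 mm or more the effect is small even for five readings. If 0.25 is a typing error, the figures fall away. All of this stands, and it is why the point is minor. It does not remove the point, because the rule as written gives up precision for no stated reason.

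It is also fair to object that LII cannot be called the most exposed outcome on the documents alone. The five-reading structure is an assumption, and arch length, also undefined, would accumulate error in the same way if measured in segments.

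Two stronger readings are tempting, and the documents support neither.
- A reader might infer that rounding biases the comparison of retainers. The same rule applies to both groups, and no between-arm bias is shown.
- A reader might infer that the 30-cast check hides the rounding error, because two readings rounded to the same step look identical. That happens only for an examiner SD of about 0.05 mm or less. At 0.10–0.20 mm reported and actual error agree. The check cannot say how much of the error is rounding, but that is not its purpose.

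**Conclusion.** The point holds as a minor loss of precision. The per-reading and per-change rounding SDs (0.072 and 0.102 mm) follow directly from the stated step, taking rounding errors as uniform and independent. The size of the consequence depends on the assumed SD of change, examiner SD and number of readings. It is modest for a five-reading LII at an SD of change near 0.5 mm, small at 1.0 mm or more, and close to nil for single-reading outcomes unless the SD of change is about 0.5 mm or less. It does not threaten the validity of the trial. It is worth acting on only because better recording costs little, and only if the display is finer than 0.25 mm.

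**What to change.** For readings still to be taken, including the 30 repeats, replace the rule with wording such as: *Measurements are recorded at the calliper's displayed resolution (stated); LII is calculated from unrounded readings; rounding is applied only in tables.* If 0.25 is a typing error, correct the figure instead.

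The cost is small: same casts, instrument and examiner. The downside is mixed resolution if earlier casts were read at 0.25 mm. The documents do not say how many have been measured. Research projects schedules the 6- and 18-month stability results for 2018, and of the 5-year project it says: "The results from this study will be presented at the Swedish Dental Congress and the European Orthodontic Society Congress in 2021". The readings still open may therefore be mainly those at 5 years, in which case only about half the loss for the T1–T4 change is recovered.

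Mixed resolution leaves the arm comparison unbiased but can shift within-group change slightly, because near-zero displacements tend to round down. Simulations with assumed displacement distributions put the shift at about 0.01 to 0.04 mm compared with rounding both casts. The report should therefore state which time points used which resolution. Re-reading T1 casts would remove the mismatch in the T1–T4 change and recover the rest of its loss, but it is real work for up to 104 patients and is optional.

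### No coding, random order or masking of casts is described, although the bonded retainer would be expected to reveal the arm on follow-up mandibular casts

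*Combined protocol and SAP*

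**What the plan says.** The stability outcomes are Little's irregularity index (LII), intercanine width, intermolar width, arch length, overjet and overbite, all read from dental casts (Materials and methods). On timing: "Dental cast are obtained at the debond appointment (T1) and at the follow-up controls after six months (T2), 18 months (T3) and 5 years (T4"). On method: "All measurements on casts are made with an electronic digital calliper to the nearest 0.25 mm".

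The arms differ in the lower jaw. In group A, "The CTC-retainer is bonded to lingual surfaces of the mandibular canines", and "The CTC-retainer is bonded to the canines directly after debonding". The comparator has nothing bonded: "Group B: Retention with Essix retainers in the maxilla and mandible". At follow-up, "The fit of the retainers and the CTC are checked at each visit".

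Two safeguards are described. Allocation is "concealed in opaque envelopes until randomization". For measurement quality, "30 randomly selected dental casts are measured by the same examiner at a five weeks interval". The Statistical analysis section then compares the arms by generalized estimating equations (GEE) with group, time and their interaction.

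The text does not say who measures the casts, what that person knows about arm or visit, or in what order the casts are read.

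**The concern.** A calliper reading on a cast depends on where the examiner places the tips. An examiner who can see the arm and expects one retainer to hold better may place them slightly differently in the two arms. The difference need not be deliberate, and its direction cannot be predicted from the documents. It would enter the group effect and the time-by-group interaction directly. It could create a difference where there is none, or hide a real one.

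The appliances cannot be hidden from the patient or from the clinician who checks their fit. A cast can be relabelled and read later, so masking is practicable at this step. The written procedure does not use that opportunity.

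**Working it through.** **1. Is masking described anywhere?** The two safeguards, set beside the measurement step:

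| Safeguard in the protocol | What it protects | Does it cover arm-dependent reading error? |
|---|---|---|
| Opaque envelopes | Allocation, up to randomisation | No; it ends before any follow-up cast exists |
| Repeat of 30 casts by the same examiner after five weeks | Repeatability | No; a consistent tilt by arm recurs at both readings and looks like good agreement |

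No other passage addresses the examiner's knowledge.

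**2. Would the arm be recognisable?** The CTC is on the lingual surfaces of the lower canines in group A only, and its fit is checked at each visit. An impression taken with it in place would be expected to reproduce it at T2, T3 and T4. This is an inference; the protocol does not state it. It fails where a CTC has been lost. At T1 it is open, because the order of bonding and impression is not given. Removing labels alone would therefore not mask every cast.

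**3. Which analyses are exposed?** Projects 1 and 3 compare the arms in the mandible, so they are exposed. Project 4 is not: a maxillary cast carries no CTC, both arms wear the same maxillary retainer, and the comparison is by diagnosis, treatment outcome, treatment time and age.

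**4. How sensitive is the comparison?** The plan has no figure to reproduce; it gives no SD, effect size or power.

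- From the documents: n = 52 per arm; significance level 0.05 (two-sided assumed, as sidedness is not stated).
- Assumed: SD of LII at one time point s = 0.8, 1.0 or 1.5 mm; average arm-dependent shift b = 0.25 or 0.10 mm; no true difference.

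Formulas, for a z-test at a single time point:

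SE = s × √(2/52) = s × 0.1961

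Type I error = Φ(b/SE − 1.96) + Φ(−b/SE − 1.96)

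| b (mm) | s (mm) | SE (mm) | b/SE | Type I error |
|---|---|---|---|---|
| 0.25 | 0.8 | 0.157 | 1.593 | 0.3570 + 0.0002 = 36% |
| 0.25 | 1.0 | 0.196 | 1.275 | 0.2466 + 0.0006 = 25% |
| 0.25 | 1.5 | 0.294 | 0.850 | 0.1335 + 0.0025 = 14% |
| 0.10 | 0.8 | 0.157 | 0.637 | 0.0930 + 0.0047 = 10% |
| 0.10 | 1.0 | 0.196 | 0.510 | 0.0735 + 0.0068 = 8% |
| 0.10 | 1.5 | 0.294 | 0.340 | 0.0526 + 0.0107 = 6% |

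**The case against.** The strongest reply is that the protocol is silent, and silence is not a statement that measurement is open. A reader might infer that the casts were read unmasked; the documents support only that no coding or masking is described. That stands. If masking is already practised, a description of it in the protocol answers the point.

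The illustration is also open to challenge. Both the shift and the SD are assumed. The 0.25 mm reading step limits rounding and is no evidence that an average bias of that size exists. The calculation is a z-test at one time point, whereas the plan is a GEE over several. The null hypotheses name no favoured retainer. All of this stands, so the figures show sensitivity and do not predict bias. At the small end, 6% is barely above nominal.

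Three further readings are tempting and are not supported:

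- That every stability outcome is affected. Project 4 is not a comparison by arm.
- That the 5-year casts are more exposed because the examiner would already know the 18-month result. The protocol gives congress years (2018 for project 1, 2021 for project 3) but no recruitment or measurement dates, so the order cannot be established.
- That cast reading is the only step that could be masked. The statistical analysis could be masked too; the protocol does not address it.

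On the remedy, a single lock across T1 to T4 would conflict with reporting project 1 before project 3, and wax might obstruct calliper placement. Both objections are sound and shape the fix below. Neither removes the gap.

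**Conclusion.** The point holds for the between-arm mandibular comparisons in projects 1 and 3. Followed as written, the procedure lets an examiner recognise the arm on follow-up casts, and its only measurement check would not detect the resulting error. This rests on the inference that a CTC in place shows on the cast, and on the absence of any described masking.

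The actual size of any bias cannot be known from the documents. Under the stated assumptions, the type I error ranges from 6% to 36% against a nominal 5%. It matters if the arm-dependent shift is of the order of a quarter of a millimetre and is minor if the shift is small. This is a worthwhile, inexpensive improvement; it is not evidence that the results are biased.

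**What to change.** Amend the cast-measurement paragraph of Materials and methods as follows.

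1. Replace patient, arm and visit labels on all casts with random codes.
2. Have the same examiner measure the casts in random order across arms and visits within each reporting batch: T1 to T3 for project 1, and T4 for project 3.
3. Keep the code key with the statistician until that batch's data are locked. Separate locks let project 1 report on schedule.
4. Cover the lingual canine-to-canine area with wax on mandibular casts in both arms, wherever this does not obstruct the measuring landmarks. Report which casts remained identifiable.

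The cost is labels, wax, a randomised measuring list, preparation time and measuring in batches. With 104 patients and four visits there are at most 104 × 4 = 416 mandibular casts to prepare: 312 in the first batch and 104 in the second. No extra assessor, visit or impression is needed.

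### The five-week repeat of 30 casts cannot show examiner drift between the 18-month and five-year reading rounds, so any drift would bias the within-group five-year mandibular change undetected

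*Combined protocol and SAP*

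**What the plan says.** Materials and methods sets the cast schedule as debond (T1) and "follow-up controls after six months (T2), 18 months (T3) and 5 years (T4) for both groups". On the instrument it says: "All measurements on casts are made with an electronic digital calliper to the nearest 0.25 mm". The reliability check is one sentence: "30 randomly selected dental casts are measured by the same examiner at a five weeks interval". It does not say when the repeat is done, which time points the 30 casts come from, how agreement is summarised, or whether the check is repeated for the T4 work. No part of the document plans to re-read early casts alongside T4, to recalibrate, or to randomise the reading order.

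Under Research projects, the mandibular outcomes of project 1 are "measured on dental casts and analysed at the debond appointment, after 6 months and after 18 months", and for that project the plan states: "The results from this study will be presented at the Swedish Dental Congress in 2018". The outcomes of project 3 are "measured on dental casts and analysed after 5 years of retention", and its results "will be presented at the Swedish Dental Congress and the European Orthodontic Society Congress in 2021".

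Materials and methods also says: "Comparisons within and between groups are performed". Statistical analysis describes post-treatment change from T1 through T4 and tests time, retention group and their interaction in a GEE model, with significance at p below 0.05.

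**The concern.** A five-year change subtracts a T1 reading from a T4 reading. If the T1 casts were read for the 2018 report and the T4 casts in a later round, the subtraction also contains any change in how the examiner reads a cast. A shift shared by all casts of the later round is completely confounded with time, and no term in the GEE model can separate the two. A repeat at five weeks falls within one round and cannot reveal it.

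At stake are the results that rest on change over time within patients: the five-year mandibular change in each arm, and the time effect in the GEE model. Overall five-year change in overjet and overbite is also exposed if project 4 reuses the readings made for project 1.

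**Working it through.** **Timing.** T4 follows T3 by 60 − 18 = 42 months for each patient. The two reports are 2021 − 2018 = 3 years apart, about 157 weeks, and 157 / 5 is about 31 times the repeat interval. T1 to T3 must be read by the 2018 presentation. That T4 is read in a separate, later round is an inference: 2018 and 2021 are presentation years, and the plan neither states nor excludes that earlier casts are re-read with T4.

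**Inputs for size.** From the documents: 52 patients per arm and a threshold of 0.05 (taken as two-sided). Assumed, because the documents give no figure: a total shift b in Little's irregularity index at T4 of 0.10 to 0.25 mm, where the upper value equals the recording step; an SD of the five-year change of 1.0 to 1.5 mm; complete follow-up; and no true change.

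**Within one arm.** SE = SD/√52, with √52 = 7.21. Rejection rate = Φ(b/SE − 1.96) + Φ(−b/SE − 1.96).

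| b (mm) | SD (mm) | SE (mm) | b/SE | Rejection rate |
|---|---|---|---|---|
| 0.10 | 1.5 | 0.208 | 0.48 | 7.7% |
| 0.10 | 1.0 | 0.139 | 0.72 | 11.1% |
| 0.25 | 1.5 | 0.208 | 1.20 | 22.5% |
| 0.25 | 1.0 | 0.139 | 1.80 | 43.8% |

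The nominal rate is 5%, so the range is about 8% to 44%.

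**Between arms.** With the same shift in both arms, a simulated t-test (20,000 runs, 52 per arm, SD 1.5 mm) gives a mean bias of 0.00 mm and rejects 5.0% to 5.1% of the time for shifts of 0.10 to 0.50 mm. If one arm carries only half the shift, the expected bias is b/2, and the rejection rate is 5.3% at b = 0.10 mm and 6.9% at b = 0.25 mm.

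**What 30 re-readings across rounds would show.** The 95% confidence half-width for the mean shift is 1.96 × SD of repeat differences / √30. An assumed SD of 0.25 mm gives 0.09 mm, and 0.5 mm gives 0.18 mm. The shift detectable with 80% power is 0.13 mm and 0.26 mm respectively.

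**The case against.** The strongest reply is that the main hypotheses are not touched. The null hypotheses of projects 1 and 3 compare the two retainers, and a shift common to both arms cancels in the time-by-group contrast, as the simulation confirms. A reader might infer that the randomised five-year comparison is biased. The documents do not support that: it would need drift that differs by arm, and nothing in the plan shows this. The protection does depend on equal drift, and the plan states neither random reading order nor masking of the examiner to arm.

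A reader might also infer that project 4, in which every patient has the same maxillary appliance, takes the full force of any drift. The documents do not support that either. Project 1 concerns the mandible, so it does not force early reading of the maxillary widths and arch length. Project 4 has no presentation date, and its casts could all be read together after T4. Its null hypothesis concerns diagnosis, treatment outcome, treatment time and age, and a common shift cancels in contrasts between patients if it is equal across the groups compared. It does not list Little's index, so the percentages above do not apply to it. What remains is overall change in overjet and overbite, if the project 1 readings are reused.

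It is also fair to say that nothing in the documents shows that drift occurs, and that its size, the SD and full follow-up are all assumed. These objections narrow the point. They do not answer it for within-group five-year change, which the plan says it will compare.

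**Conclusion.** The point holds in a limited form. The stated check cannot detect drift between reading rounds. If the T4 casts are read in a later round than T1 to T3, any drift would pass undetected into the within-group five-year mandibular change and the GEE time effect. Under the stated assumptions, the false-positive rate of a within-arm test on Little's index would be about 8% to 44% instead of 5%. These figures illustrate sensitivity and do not estimate what happened. The conclusion rests on inferred separate rounds and on drift that is possible but not demonstrated. It is an inexpensive improvement to a secondary set of results and leaves the randomised comparison standing, provided that drift is equal in the two arms.

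**What to change.** Add a sentence to Materials and methods. When the T4 casts are read, the same examiner re-reads at least 30 randomly chosen T1 to T3 casts already measured for project 1, mixed with the T4 casts in random order. The mean shift is reported with its confidence interval and limits of agreement beside the within-group five-year change. The interval matters more than a test, because 30 casts may not detect a shift as small as 0.10 mm.

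Preferably, re-read all stored T1 casts (up to 104) in this way and compute the five-year change from the paired readings, so that a shift common to the round drops out. T2 and T3 would remain first-round readings, so the estimated shift is still needed to interpret the step from T3 to T4.

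The cost is measuring time, with no patient contact, new visit or extra staff. If all T1 casts are re-read, the T1 values will differ slightly between the 18-month and five-year reports, and the later report should say so.
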